4.22 History of allergy to study drug components

4.23 Prior immune checkpoint targeting drugs (e.g., anti PD1, anti PDL1, anti-kir, anti CD137...etc)

5.0 Treatment Plan

5.1 **General:** All patients should be registered with PDMS. Information pertaining to important prognostic factors such as age, performance status and prior therapy will be recorded.

5.2 **Treatment Schedule:** (Each cycle is approximately 28-35 days)

a. **Phase I**

Nivolumab dosed as indicated below starting approximately on day 24 ± 2 days

Idarubicin 12 mg/m² IV over 15 to 30 minutes daily x 3 (days 1-3)

ara-C 1.5 g/m² IV over 24 hours daily (days 1-4)

Solumedrol 50 mg or dexamethasone 10 mg IV daily for 3-4 days with ara-C (days 1-4)

All patients may receive a second induction course at the discretion of treating physician.

The dose of investigational agent, that is, Nivolumab, will be escalated in successive cohorts of patients. Patients will be entered sequentially to each dose level. If none of the first 3 patients at a dose level experience first cycle dose-limiting toxicity (DLT), new patients may be entered at the next higher dose level. If 1 of 3 patients experience first cycle DLT, up to 3 more patients are started at that same dose level. If 1 of 6 experience DLT, then new patients may be entered at the next higher dose level. If 2 or more experience first cycle DLT, no further patients are started at that dose. The MTD is the highest dose level in which <2 patients of 6 develop first cycle DLT. The following table lists out the 3 dosage levels that will be used in the study, and the starting dose is 1mg/kg IV of Nivolumab. There will be no intra-patient dose escalation for Nivolumab.

The enrollment of participants will be staggered; all the participants in each cohort will be observed for approximately 3 weeks from the first dose of Nivolumab before proceeding to the next cohort.

Dose of nivolumab will be as follows:

Dose level	Nivolumab (mg/kg IV)	No of patients
-1	0.3	3
0	1	3
1	3	3

b. **Phase II** (Each cycle is approximately 28-35 days)

Patients will receive 1 or 2 induction cycles of therapy according to the following starting schedule:

Nivolumab starting approximately on day 24 \pm 2 days at a dose defined by Phase I portion of the study but it is expected that the dose 3 mg/kg will be selected based on prior studies.

Idarubicin 12 mg/m² IV over 15 to 30 minutes daily x 3 (days 1-3)

ara-C 1.5 g/m² IV over 24 hours daily (days 1-4) (days 1-3 for patients older than 60)

Solumedrol 50 mg or dexamethasone 10 mg IV daily for 3-4 days with ara-C (days 1-4) (days 1-3 for patients older than 60).

Nivolumab will be administered at approximately 2 week intervals for up to 1 year.

5.3 Dose modifications during phase II:

Patients who experience nivolumab-specific (defined as determined by the principal investigator) grade 3-4 extramedullary toxicities during induction cycle #1, and who are not in CR after cycle #1, may receive a second induction course at a similar or lower dose level with respect to idarubicin and cytarabine. Other dose modification schedules felt to be in the best interest of the patient may be permitted, after discussion with the principal investigator. There will be no dose modifications of idarubicin or cytarabine for either induction cycle #1, or second induction course, secondary to myelosuppression. There will be no dose reduction with respect to Nivolumab but dose delays or interruptions are permitted after discussion with the PI.

5.4 Administration guidelines for nivolumab: Nivolumab will be administered by IV infusion over approximately 60 minutes \pm 10 minutes. The recommended infusion duration for the product is 60 minutes and every effort should be made to adhere to this time as closely as possible.

5.5 No dose reduction is allowed for Nivolumab. Dose delays and interruptions should follow the guidance in section 6.10.3.

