- 5.9.1 If judged more beneficial for patient care and disease control, patients may have dose reductions to allow for continuation of therapy with acceptable myelosuppression.
- 5.9.2 The dose of chemotherapy treatment (ie idarubicin/cytarabine) in subsequent courses will be reduced by 25% for grade 3-4 extramedullary toxicities, or for severe life-threatening infections.
- 5.9.3 In responding patients, courses will be given at 4 to 6 week intervals provided the granulocyte count has recovered to $> 1.0 \times 10^9/L$ and the platelet count to $> 50 \times 10^9/L$. In patients with persistent disease, therapy could be restarted once counts recover to the pretreatment values.
- 5.9.4 Dose adjustments for only one of the drugs can be made if, in the opinion of the treating physician, the toxicity is attributable to one of the drugs.

- 5.10 **Administration guidelines for consolidation/maintenance nivolumab:**
Nivolumab will be administered IV approximately every 2 weeks starting from day 24 ± 2 days of first induction course. If a dose is missed, the next dose will not be increased to account for missing a dose. The patient will take the next regular dose at the regularly scheduled time.

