12.2 Phase I study

The 3+3 design will be used to identify the MTD of nivolumab. The following table lists out the 3 dosage levels that will be used in the study, and the starting dose is 1mg/kg IV

of Nivolumab With 3 doses, the maximum total number of patients for phase I part will be 12 patients.

The dose of treatment agent, that is, Nivolumab, will be escalated in successive cohorts of patients. Patients will be entered sequentially to each dose level. If none of the first 3 patients at a dose level experience first cycle dose-limiting toxicity (DLT), new patients may be entered at the next higher dose level. If 1 of 3 patients experience first cycle DLT, up to 3 more patients are started at that same dose level. If 1 of 6 experience DLT, then new patients may be entered at the next higher dose level. If 2 or more experience first cycle DLT, no further patients are started at that dose. The MTD is the highest dose level in which <2 patients of 6 develop first cycle DLT.

Table 13.1 Dose levels of nivolumab

Dose level	Nivolumab (mg/kg IV)
-1	0.3
0	1
1	3

Prior to advancing/changing dose levels, a cohort summary will be completed and submitted to the IND Office Medical Monitor for review and approval.

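### Escalation and the MTD count only first-cycle DLTs: as worded, about 4–11 days after the first nivolumab dose count, although each cohort is already held for about 3 weeks from that dose

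*Combined protocol and SAP*

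**What the plan says.** Section 5.2a gives the rule for moving up a dose level: "If none of the first 3 patients at a dose level experience first cycle dose-limiting toxicity (DLT), new patients may be entered". Section 12.2 repeats it and closes with "The MTD is the highest dose level in which <2 patients of 6 develop first cycle DLT". One sentence of the rule, present in both sections, leaves out the cycle restriction: "If 1 of 6 experience DLT, then new patients may be entered at the next higher dose level".

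Three timing statements bear on what this restriction means:

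- Cycle length, section 5.2: "Each cycle is approximately 28-35 days".
- First nivolumab dose, section 5.2a: "Nivolumab dosed as indicated below starting approximately on day 24", with a window of ± 2 days.
- Cohort hold, section 5.2a: all participants in a cohort "will be observed for approximately 3 weeks from the first dose of Nivolumab before proceeding to the next cohort".

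On repeat dosing, section 5.2 says "Nivolumab will be administered at approximately 2 week intervals for up to 1 year", and section 5.10 gives the same interval counted from day 24 of the first induction course. Section 13.1.6 sets a minimum gap of 12 days between doses. For course spacing, section 5.9.3 says "In responding patients, courses will be given at 4 to 6 week intervals provided the granulocyte count has recovered".

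Section 5.11 defines DLTs by type and grade and gives no observation window for escalation. Section 12.2 does not mention the 3-week hold.

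**The concern.** Phase I exists to choose the nivolumab dose, yet nivolumab arrives near the end of the only cycle in which DLTs are counted. The count therefore covers a short period after first exposure, and its length depends on when the next chemotherapy course starts rather than on time since nivolumab.

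Suppose a drug-related grade 3 non-haematologic event occurs on day 40. It falls inside the hold and the trial sees it, but under the written rule it is not a first-cycle DLT if cycle 1 ended by day 35. Two careful readers could then reach different escalation decisions, and different MTDs, from the same data.

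The chosen dose goes into phase II for up to a year. Sections 5.3, 5.5 and 5.10.3 allow no nivolumab dose reduction, so a dose set too high can only be delayed, interrupted or stopped in an individual patient.

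**Working it through.** The plan states no figure for the number of days counted. The only computed phase I figure is the maximum of 12 patients in section 12.2. It follows from two levels on a direct path with up to 6 patients each (6 + 6 = 12), and the window does not affect that sum.

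**Step 1. Days after first nivolumab that fall in cycle 1.** Inputs: first dose on day 24 (22–26) and cycle end on day 28 or 35 (section 5.2). The 42-day column is a check that borrows the upper course interval in section 5.9.3. Formula: days counted = last day of cycle 1 − day of first dose. Dose 2 = first dose + 14. Hold end = first dose + 21.

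| First dose | 28-day cycle | 35-day cycle | 42-day cycle | Dose 2 | Hold ends |
|---|---|---|---|---|---|
| Day 22 | 6 | 13 | 20 | Day 36 | Day 43 |
| Day 24 | 4 | 11 | 18 | Day 38 | Day 45 |
| Day 26 | 2 | 9 | 16 | Day 40 | Day 47 |

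As shares of the 21-day hold:

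- At nominal day 24: 4/21 = 19% to 11/21 = 52%.
- At the extremes: 2/21 = 10% to 13/21 = 62%.
- With a 6-week first cycle: 16/21 = 76% to 20/21 = 95%.

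At 14-day spacing, dose 2 (day 36–40) falls after a 28–35 day cycle. It falls inside a 6-week cycle. With the 12-day minimum gap and a day-22 start, it could come on day 22 + 12 = 34, just inside a 35-day cycle. Hence the count normally, but not always, ends before dose 2.

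**Step 2. What this can do to escalation (illustration only).** The documents give no DLT rate or onset pattern. Assume a risk P spread evenly over the 21-day hold and no DLT before nivolumab. With d days counted, q = P × d/21. A level is cleared with 0 of 3 DLTs, or with 1 of 3 followed by 0 of 3:

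clearance = (1 − q)³ + 3q(1 − q)⁵

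For P = 0.10 and d = 21, q = 0.10 and clearance = 0.729 + 0.3 × 0.590 = 0.906.

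| P over 21 days | All 21 days count | 4 to 11 days count | 16 to 20 days count |
|---|---|---|---|
| 10% | 0.906 | 0.996 to 0.971 | 0.942 to 0.914 |
| 20% | 0.709 | 0.984 to 0.898 | 0.809 to 0.729 |

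**Step 3. Sensitivity to onset, at P = 20%.**

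- Constant hazard, q = 1 − (1 − P)^(d/21): clearance is 0.981 to 0.889 for 4 to 11 days, against 0.709 for 21 days.
- Rising hazard (Weibull, shape 2), q = 1 − (1 − P)^((d/21)²): 0.999 to 0.963, against 0.709.
- The same 20% spread over 42 days, q = P × d/42: 0.996 to 0.971 for 4 to 11 days, but still 0.906 for 21 days. A 21-day window therefore misses later onset too.

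**The case against.** The strongest reply is that the hold was meant to be the DLT window. It comes directly after the escalation rule, it governs the move to the next cohort, and it has little other purpose. One rule sentence omits the cycle restriction, and all three timings are approximate. This is plausible and cannot be excluded. But the text never says it, section 12.2 states the rule without the hold, and the restriction is repeated in the MTD definition. If it was the intention, the amendment simply records it.

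Second, there are safeguards. The Medical Monitor must approve a cohort summary before any dose change (section 12.2). Phase II monitors nivolumab-attributable grade 3–4 toxicity by 12 months against a 10% limit (section 12.3). Only one upward step exists, from 1 to 3 mg/kg, and section 5.2b already expects 3 mg/kg. These points limit the consequences, but none of them alters what counts as a DLT for escalation.

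Third, cycle 1 starts on day 1, not day 24. Section 5.11(a) refers to drug-related toxicity and objective 3.1 to tolerability of the combination, so events on days 1–23 count now. This stands, and a new window that began only at the first nivolumab dose would lose them.

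A reader might go further and infer that DLTs after cycle 1 would be disregarded in practice, or that the selected dose would be wrong. The documents do not support either: they describe a rule, not how reviewers would handle a known event in the hold, and they give no DLT rate. A reader might also want the 6-week haematologic criterion in section 5.11(b) removed because it matures late. That would weaken a safety criterion for a combination regimen. Whether that event can be known before escalation is a separate issue.

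**Conclusion.** The concern holds as a mismatch between the counting rule and the observation the protocol already requires. Followed as worded, the rule uses about 4–11 of the roughly 21 days of post-nivolumab observation (2–13 at the extremes), normally before dose 2. If cycle 1 ran to 6 weeks, 16–20 days would count and the gap would nearly close.

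The day counts rest only on the stated schedule and are firm. The clearance probabilities rest on assumed risks and onset patterns; they show direction, with a modest gap at 10% risk and a larger one at 20%. This should be fixed because the phase II dose depends on the count.

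**What to change.** In every escalation and MTD sentence of sections 5.2a and 12.2, including the 1-of-6 sentence that now has no time limit, define the event as *DLT from day 1 of cycle 1 through the later of the end of cycle 1 and the end of the approximately 3-week observation after the first nivolumab dose*.

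This keeps pre-nivolumab combination toxicity in the count and adds the rest of the hold. With cycles of 28–35 days, or even 42, the later date is the end of the hold (day 43–47), so no waiting time is added.

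The new window contains the current first-cycle window, so the count can only rise and escalation becomes somewhat less likely: in the 10% illustration, 0.91 rather than 0.97–0.996. Events that start after the hold remain outside the count. Section 5.11(b) stays as it is under this change.

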5.6 Myelosuppression

Patients with acute leukemia usually present with abnormal peripheral blood counts at the time therapy is started, and myelosuppression is an expected event during the course of therapy for acute leukemias and myelodysplastic syndromes. Thus, no dose adjustments or treatment interruptions for myelosuppression will be planned for the first 6 weeks of therapy. After this time, treatment interruptions and dose adjustments may be considered according to the following guidelines:

Patients with neutropenia or thrombocytopenia as a consequence of the disease prior to the start of therapy do not require treatment interruptions for myelosuppression. Dose reductions of the chemotherapy agents in these patients should be considered on an individual case basis and discussed with the PI.

Nivolumab is not associated with myelosuppression – it can be held if necessary but no dose reductions are needed after resumption

- 5.7 **Dose adjustments for only one of the drugs** can be made if, in the opinion of the treating physician, the toxicity is attributable to one of the drugs.
- 5.8 Patients who show no significant anti-tumor effect (i.e. no CR or CRp) after 2 courses will be taken off the study.
- 5.9 **Remission Consolidation/Maintenance:** Patients achieving a CR or CRp may receive consolidation maintenance therapy as follows:
 - a. Consolidation – Up to 5 additional courses as follows:
 - Idarubicin 8 mg/m² IV over 15 to 30 minutes daily x 2 days (or the final induction dose, whichever is lower).(days 1-2)
 - Ara-C 0.75 g/m² IV over 24 hours daily x 3 days (or the final induction dose, whichever is lower) (days 1-3)
 - Nivolumab dose as per induction IV every 2 weeks as a continuation of the induction treatment.
 - Solumedrol 50-100 mg or dexamethosone 10 mg IV daily x 3 days with ara-C (days 1-3)
 - courses given every 4-6 weeks upon recovery of counts and toxicities
 - b. Maintenance – Nivolumab will be administered every 2 weeks for up to 1 year with no breaks except for toxicity. Maintenance will only be administered in patients in CR or CRp.
 - c. Consideration of allogeneic transplant in CR. Patients eligible for allogeneic.

SCT will be evaluated for the procedure, if felt to be in their best interest. Therapy with nivolumab will be discontinued at least approximately one week prior to admission for the transplant procedure.

- 5.9.1 If judged more beneficial for patient care and disease control, patients may have dose reductions to allow for continuation of therapy with acceptable myelosuppression.
- 5.9.2 The dose of chemotherapy treatment (ie idarubicin/cytarabine) in subsequent courses will be reduced by 25% for grade 3-4 extramedullary toxicities, or for severe life-threatening infections.
- 5.9.3 In responding patients, courses will be given at 4 to 6 week intervals provided the granulocyte count has recovered to $> 1.0 \times 10^9/L$ and the platelet count to $> 50 \times 10^9/L$. In patients with persistent disease, therapy could be restarted once counts recover to the pretreatment values.
- 5.9.4 Dose adjustments for only one of the drugs can be made if, in the opinion of the treating physician, the toxicity is attributable to one of the drugs.

- 5.10 **Administration guidelines for consolidation/maintenance nivolumab:**
Nivolumab will be administered IV approximately every 2 weeks starting from day 24 ± 2 days of first induction course. If a dose is missed, the next dose will not be increased to account for missing a dose. The patient will take the next regular dose at the regularly scheduled time.

5.10.1 Patient Monitoring During Infusion

Initial dose vital signs should be monitored prior to dosing, approximately every 30 minutes after initiation of infusion, and up to approximately 60 minutes after the completion of the infusion, or longer if indicated, until the vital signs normalize or return to baseline. For subsequent infusions, vital signs should be collected prior to dosing, and at the completion of the infusion. If the patient experiences an infusion reaction, the patient will be monitored for up to 60 minutes after the completion of the infusion, or longer if indicated, until the vital signs normalize or return to baseline. A +/- 30 minute window applies to all vital signs time points.

5.10.2 Treatment of nivolumab Related Infusion Reactions

Since nivolumab contains only human immunoglobulin protein sequences, it is unlikely to be immunogenic and induce infusion or hypersensitivity reactions. However, if such a reaction were to occur, it might manifest with fever, chills, rigors, headache, rash, pruritis, arthralgia's, hypo- or hypertension, bronchospasm, or other symptoms. All Grade 3 or 4 infusion reactions should be reported within 24 hours to the BMS Medical Monitor and reported as an SAE if criteria are met. Infusion reactions should be graded according to NCI CTCAE (version 4.03) guidelines.

Treatment recommendations for nivolumab related infusion reactions are provided below and may be modified based on MD Anderson treatment standards and guidelines, as appropriate:

For Grade 1 symptoms (Mild reaction; infusion interruption not indicated; intervention not indicated): Remain at bedside and monitor subject until recovery from symptoms. The following prophylactic premedications are recommended for future infusions: diphenhydramine 50 mg (or equivalent) and/or acetaminophen 325 to 1000 mg at least 30 minutes before additional nivolumab administrations.

For Grade 2 symptoms (Moderate reaction requires therapy or infusion interruption but responds promptly to symptomatic treatment [e.g. antihistamines, non-steroidal anti-inflammatory drugs, narcotics, corticosteroids, bronchodilators, IV fluids]; prophylactic medications indicated for ≤ 24 hours):

Stop the nivolumab infusion, begin an IV infusion of normal saline, (at approximately 40cc/hour but adjusted according to the clinical situation to ensure stabilization of blood pressure) and treat the subject with diphenhydramine 50 mg IV (or equivalent) and/or acetaminophen 325 to 1000 mg; remain at bedside and monitor subject until resolution of symptoms. Corticosteroid or bronchodilator therapy may also be administered as appropriate. If the infusion is interrupted, then restart the infusion at 50% of the original infusion rate when symptoms resolve; if no further complications ensue after 30 minutes, the rate may be increased to 100% of the original infusion rate. Monitor subject closely. If symptoms recur then no further nivolumab will be administered at that visit. Administer diphenhydramine 50 mg IV, and remain at bedside and monitor the subject until resolution of symptoms. The amount of study drug infused must be recorded on the case report form (CRF). The following prophylactic premedications are recommended for future infusions: diphenhydramine 50 mg (or equivalent) and/or acetaminophen 325 to 1000 mg should be administered at least 30 minutes before additional nivolumab administrations. If necessary, corticosteroids (recommended dose: up to 25 mg of IV hydrocortisone or equivalent) may be used.

For Grade 3 or Grade 4 symptoms [Severe reaction, Grade 3: prolonged (i.e. not rapidly responsive to symptomatic medication and/or brief interruption of infusion); recurrence of symptoms following initial improvement; hospitalization indicated for other clinical sequelae (e.g. renal impairment, pulmonary infiltrates), Grade 4: life-threatening; pressor or ventilatory support indicated]:

Immediately discontinue infusion of nivolumab. Begin an IV infusion of normal saline, (at approximately 40cc/hour but adjusted according to the clinical situation to ensure stabilization of blood pressure) and treat the subject as follows: Recommend bronchodilators, epinephrine 0.2 to 1 mg of a 1:1,000 solution for subcutaneous administration or 0.1 to 0.25 mg of a 1:10,000 solution injected slowly for IV administration, and/or diphenhydramine 50 mg IV with methylprednisolone 100 mg IV (or equivalent), as needed. Subject should be monitored until the investigator is

comfortable that the symptoms will not recur. Nivolumab will be permanently discontinued. Institutional guidelines will be followed for the treatment of anaphylaxis. Remain at bedside and monitor subject until recovery from symptoms. In the case of late-occurring hypersensitivity symptoms (e.g. appearance of a localized or generalized pruritus within 1 week after treatment), symptomatic treatment may be given (e.g. oral antihistamine or corticosteroids).

For further details regarding dose-calculation of nivolumab, preparation and dispensing of nivolumab, administration of nivolumab please see the dosing procedure manual.

5.10.3 Nivolumab dose delay for immune-oncology drug-related adverse events, clinically significant in the opinion of the investigator

Nivolumab administration should be delayed for the following drug-related AEs:

- Any Grade >2 non -skin AE, except that
 - Grade 2 fatigue or laboratory abnormalities do not require delay, however
 - ◆ For a subject with baseline AST, ALT, or total bilirubin within normal limits, delay dosing for drug-related Grade >2 values
- Any Grade 3 skin AE, or Grade 3 laboratory abnormality, with the following exceptions:
 - Grade 3 lymphopenia or leukopenia does not require dose delay.
 - If a subject has Grade 1 baseline AST, ALT, or total bilirubin, delay dosing for drug-related Grade 3 toxicity
- Any AE, laboratory abnormality, or intercurrent illness, which in the judgment of the investigator, warrants delaying the dose of study medication.
- Nivolumab dose reductions are not permitted in this study (only dose delays when indicated).

Detailed management algorithms for immune-oncology drug-related adverse events (including gastrointestinal, renal, pulmonary, hepatic, endocrine, skin and neurological) are provided in Appendix E. These general guidelines constitute guidance to the Investigator and may be supplemented by discussions with the Medical Monitor representing the Sponsor. If the criterion to resume treatment is met, the subject should restart treatment at the next scheduled time-point per protocol.

Criteria to Resume Treatment:

Subjects may resume treatment with study drug when the drug-related AE(s) resolve to Grade ≤1 or baseline value, with the following exceptions:

- Subjects may resume treatment in the presence of Grade 2 fatigue
- Subjects who have not experienced a Grade 3 drug-related skin AE may resume treatment in the presence of Grade 2 skin toxicity

- Subjects with baseline Grade 1 AST/ALT or total bilirubin who require dose delays for reasons other than a 2-grade shift in AST/ALT or total bilirubin may resume treatment in the presence of Grade 2 AST/ALT OR total bilirubin
- Subjects with combined Grade 2 AST/ALT AND total bilirubin values meeting discontinuation parameters (Discontinuation Section below) should have treatment permanently discontinued
- Drug-related pulmonary toxicity, diarrhea, or colitis, must have resolved to baseline before treatment is resumed
- Drug-related endocrinopathies adequately controlled with only physiologic hormone replacement may resume treatment

If the criteria to resume treatment are met, the subject should restart treatment at the next scheduled timepoint per protocol. However, if the treatment is delayed past the next scheduled timepoint per protocol, the next scheduled timepoint will be delayed until dosing resumes.

If treatment is delayed > 6 weeks, the subject must be permanently discontinued from study therapy, except as specified in discontinuation section.

Nivolumab Discontinuation Criteria:

Treatment should be permanently discontinued for the following:

- Any Grade 2 drug-related uveitis or eye pain or blurred vision that does not respond to topical therapy and does not improve to Grade 1 severity within the re-treatment period OR requires systemic treatment
- Any Grade 3 non-skin, drug-related adverse event lasting > 7 days, with the following exceptions for drug-related laboratory abnormalities, uveitis, pneumonitis, bronchospasm, diarrhea, colitis, neurologic adverse event, hypersensitivity reactions, and infusion reactions:
 - Grade 3 drug-related uveitis, pneumonitis, bronchospasm, diarrhea, colitis, neurologic adverse event, hypersensitivity reaction, or infusion reaction **of any duration** requires discontinuation
- Grade 3 drug-related laboratory abnormalities do not require treatment discontinuation except those noted below:
 - Grade 3 drug-related thrombocytopenia > 7 days or associated with bleeding requires discontinuation
 - Any drug-related liver function test (LFT) abnormality that meets the following criteria require discontinuation:
 - AST or ALT > 8 x ULN
 - Total bilirubin > 5 x ULN
 - Concurrent AST or ALT > 3 x ULN and total bilirubin > 2 x ULN

- Any Grade 4 drug-related adverse event or laboratory abnormality, except for the following events which do not require discontinuation:
 - Isolated Grade 4 amylase or lipase abnormalities that are not associated with symptoms or clinical manifestations of pancreatitis and decrease to < Grade 4 within 1 week of onset.
 - Isolated Grade 4 electrolyte imbalances/abnormalities that are not associated with clinical sequelae and are corrected with supplementation/appropriate management within 72 hours of their onset
- Any dosing interruption lasting > 6 weeks with the following exceptions:
 - Dosing interruptions to allow for prolonged steroid tapers to manage drug-related adverse events are allowed. Prior to re-initiating treatment in a subject with a dosing interruption lasting > 6 weeks, the Investigator must be consulted. Tumor assessments should continue as per protocol even if dosing is interrupted
 - Dosing interruptions > 6 weeks that occur for non-drug-related reasons may be allowed if approved by the Investigator. Prior to re-initiating treatment in a subject with a dosing interruption lasting > 6 weeks, the Investigator must be consulted. Tumor assessments should continue as per protocol even if dosing is interrupted
- Any adverse event, laboratory abnormality, or intercurrent illness which, in the judgment of the Investigator, presents a substantial clinical risk to the subject with continued nivolumab dosing

5.11

Definition of Dose Limiting Toxicity (DLT)

Dose-Limiting Toxicity will be graded according to the NCI Common Toxicity Criteria version4.03. See NCI Common Toxicity Criteria for definitions of DLT by organ system.

- a) All \geq grade 3 drug-related, clinically significant non-hematologic toxicities will be considered DLTs. A study drug-related occurrence of an elevation in AST/ALT $> 3 \times$ ULN and concomitant Bilirubin of $> 2 \times$ ULN is a Dose Limiting Toxicity and patients meeting this criteria should be permanently discontinued from study treatment (nivolumab).
As the following are common events in patients with leukemia (> 50%), they will not be used for the definition of MTD and DLT, nor will they be reported as ADRs: low blood pressure due to dehydration requiring fluid replacement, abnormalities of LDH (lactate dehydrogenase) and alkaline phosphatase, disturbances in electrolytes (magnesium, phosphorus,

calcium), alopecia, nausea and vomiting (if manageable with supportive care measures).

b) Grade 3 hematologic toxicity (criteria for leukemia on the CTC version 3.0) lasting for 6 weeks or more after interruption of therapy with a hypocellular bone marrow and no marrow blasts. Anemia will not be considered a hematologic DLT. As the following are common events in patients with leukemia (> 50%), they will not be used for the definition of MTD and DLT, nor will they be reported as ADRs: prolonged myelosuppression (grade 3 - 4), neutropenic fever without infection (grade 3), non-neutropenic fever (grade 3), infections with grade 3 and 4 neutropenia, infections without neutropenia (grade 3), readmission associated with NCI grade 3 toxicity cytopenias not resulting in death, transfusions of platelets and packed RBCs (grade 3).

5.12

Concomitant medications: In the event of severe anemia, thrombocytopenia or neutropenia, patients may receive appropriate supportive care (e.g., transfusions, prophylactic antibiotics, antifungals and/or antivirals, hematopoietic growth factors). In the event of high white blood cell (WBC) counts, patients may receive hydroxyurea (at any dose) or 1 dose of cytarabine (up to \leq 2g) prior to start of study treatment in order to keep their WBC at an acceptable level while being evaluated for the study. During the trial they may undergo leukopheresis for the same purpose.

Concomitant administration of any other therapy specific for MDS or AML, including any use of systemic retinoids, is prohibited. Concomitant administration of any other anticancer therapy is prohibited. Intrathecal chemotherapy is allowed, when indicated.

Subjects may receive anti-infective prophylaxis according to institutional practices. Use of recombinant myeloid colony stimulating factors (CSF) is allowed, if patients have febrile neutropenia or documented infections.

Concomitant medications will be recorded in the medical records only.

